MAPS is a holistic, dynamic approach to facilitating behavior change that utilizes a combined motivational enhancement and social cognitive approach based on motivational interviewing (MI)^{18,19} and social cognitive theory.²⁰⁻²² MAPS is designed for all individuals regardless of their readiness to change, and specifically targets motivation and intrinsic motives for change, social cognitive constructs (e.g., agency/self-efficacy), and other factors of key relevance to cervical cancer survivors (e.g., stressors, anxiety, depression, family conflicts, finances, fear of cancer recurrence). Because MAPS revolves around a Wellness Program that addresses numerous barriers and concerns that are prevalent among cervical cancer survivors, we believe it is particularly appropriate for treating this population. Furthermore, the delivery of this intervention via telephone offers a less resource intensive modality while also minimizing participant burden.

The specific aims are to:

1. Compare the efficacy of a MAPS approach to promoting and facilitating smoking cessation to ST among cervical cancer survivors.
2. Assess the effects of MAPS on hypothesized treatment mechanisms (motivation, agency, and stress/negative affect) and the role of those mechanisms in mediating MAPS effects on abstinence.
3. Compare the cost-effectiveness of MAPS and ST.

SIGNIFICANCE

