Assessment calls will occur at Baseline and at 3, 6, 12, and 18 months after Baseline. The primary outcomes are abstinence from tobacco at the 18-month follow-up and abstinence across all follow-ups. Secondary outcomes are smoking quit attempts, cigarettes per day, use of the quitline, and cost-effectiveness. Participants will be scheduled to complete a baseline assessment call within one week. Following the baseline assessment, participants will be randomly assigned to ST or MAPS. Participants will schedule their first counseling call at that time (see Table 1).

Recruitment. Participants will be women with a diagnosis of cervical cancer or high grade cervical dysplasia who report smoking any cigarettes within the past 30 days, recruited through the Stephenson Cancer Center or OU Physicians at the University of Oklahoma Health Sciences Center, via the ClinicalTrials.gov website, by responding to recruitment flyers and internet advertisements (e.g., flyers in clinics, Facebook), and through referrals from healthcare providers.

Participant Eligibility. Inclusion criteria: ≥ 18 ; current smoker with a history of at least 100 lifetime cigarettes and a self-report of smoking within the last 30 days; history of cervical cancer or high grade cervical dysplasia (we have defined survivorship as beginning at the time of cancer diagnosis, consistent with the NCI definition); has a working cell phone; valid home address; speaks English, Spanish or both languages. Exclusion criteria: current use of tobacco cessation medications; self-report of being pregnant or lactating; or, another household member enrolled in the study; or contraindication of nicotine patch use unless under the supervision of a physician as advised by project staff.

Table 1. Schedule of Study Procedures and Assessments	Screening	Baseline	Month 3	Month 6	Month 12	Month 18
Inclusion/Exclusion Criteria	X	X				
Compensation		\$60	\$60	\$60	\$60	\$60
TREATMENT PROCEDURES						
Standard Treatment (ST)	Delivered at Baseline, and Months 6 and 12					
Motivation And Problem Solving (MAPS)	ST plus up to 6 MAPS Counseling Calls delivered over 12 months					
DEMOGRAPHICS, MENTAL HEALTH						
Demographics and Smoking History		X				
Cancer stage at diagnosis, time since diagnosis, current stage, treatment status	X					
Subjective Social Status		X	X	X	X	X
Fear of Cancer Recurrence Inventory (FCRI)	X	X	X	X	X	X
MOTIVATION						
Contemplation Ladder		X	X	X	X	X

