Financial Compensation and Retention Procedures. Participants will receive financial remuneration after completing each assessment call to compensate for the time and inconvenience associated with participation (\$60 for each of the 5 assessment calls and up to a total of \$300). The inclusion of compensation makes study participation more feasible and acceptable, which increases the representativeness of the sample and generalizability of the results. Compensation also increases follow-up rates, which reduces biases, and we have consistently achieved follow-up rates of approximately 80% even among very low-SES and racially/ethnically diverse smokers.^{69,102} Other procedures to reduce attrition include: 1) mailing postcard reminders and calling to remind participants of upcoming assessment calls; 2) maintaining communication with participants throughout the study period via mailing birthday cards, holiday cards, etc. (each mailing includes a stamped address update postcard with the study return address); 3) Having a staff member available at all times during business hours as well as evenings and weekends to conduct assessment calls; 4) requiring that in addition to a functional phone number (necessary for counseling calls), participants must have a home address so that they can be contacted by mail if necessary; and 5) obtaining names, addresses, and phone numbers of up to three collaterals (i.e., relatives/friends) who can provide information on participants' whereabouts during the study (permission to contact the collaterals will be obtained from participants). In addition to being compensated for the time associated with completing assessments, all participants will be compensated up to a total of \$150 for completing the assessments, up to a total of \$150 for costs incurred as a result for the use of study-related cell phone minutes, and up to a total of \$120 for returning the cotinine tests. Compensation for completing assessments will be provided at baseline, 3, 6, 12, and 18 months from baseline (5 times points x \$30 = \$150). Compensation for study-related cell phone use will be provided at baseline, 3, 6, 12, and 18 months from baseline (5 time points x \$30 = \$150). Compensation for returning the cotinine tests will be provided at 3, 6, 12, and 18 months (4 time points x \$30 = \$120).

TREATMENT PLAN

Nicotine Replacement. All participants are eligible to receive a 12-week supply of nicotine patches and

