lozenges. Participants will receive educational materials describing potential side effects; proper use of the patch and an illustration demonstrating the proper placement of the patch on the body. The nicotine patch and lozenge regimen will be based on the participant's self-reported smoking rate and will not be validated once assigned. At the time of enrollment, a research staff member will determine the proper dose. Participants who smoke >10 cigarettes/day will receive 8 weeks of 21 mg. patches, 2 weeks of 14 mg. patches, 2 weeks of 7 mg. patches, and 12 weeks of 2 mg. lozenges. Those who smoke <10 cigarettes/day will receive 8 weeks of 14 mg. patches, 4 weeks of 7 mg patches, and 12 weeks of 2 mg. lozenges.

Standard Treatment (ST). ST will consist of 1) a mailed packet of materials including a letter referring smokers to the quitline, 2) free nicotine replacement therapy when they are ready to quit, and 3) standard self-help materials. ST will be delivered a total of 3 times to participants with completed assessments (at Baseline, 6 and 12 months).

MAPS. MAPS will consist of ST plus up to 6 proactive telephone counseling sessions over a 12-month period. Each call will last approximately 30 minutes. Calls are scheduled based on participants' needs in negotiation with the counselor. For example, call timing can be negotiated to be clustered around the timing of a specific quit attempt. This is consistent with many interventions that load treatment during the period when relapse risk is highest.¹⁰³ Similarly, a woman not motivated to quit might negotiate the next call to occur many months later, or to occur sooner if specific barriers are noted that the individual wishes to address (e.g., stress, social support, family problems). Similarly, individuals struggling with maintaining abstinence may have several calls in a shorter period of time to get them through the problematic period, while others need less frequent help.

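### No stated re-check of pregnancy, lactation or patch contraindication before nicotine replacement is released after baseline

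*Combined protocol and SAP*

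**What the plan says.** **Supply.** The Treatment Plan, under Standard Treatment (ST), lists three components: a quitline referral packet, "free nicotine replacement therapy when they are ready to quit", and self-help materials. The schedule follows: "ST will be delivered a total of 3 times to participants with completed assessments (at Baseline, 6 and 12 months". MAPS is ST plus up to six counseling calls, so the NRT provision applies to both arms. Under Nicotine Replacement, "All participants are eligible to receive a 12-week supply of nicotine patches", together with lozenges. Dose is set at enrollment from the reported smoking rate, and women receive educational material on side effects and on using the patch.

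**Entry safeguards.** Participant Eligibility excludes women on "self-report of being pregnant or lactating", with no exception, and on "contraindication of nicotine patch use unless under the supervision of a physician as advised by project staff". In Table 1 the row "Inclusion/Exclusion Criteria" is marked at Screening and Baseline and is blank at months 3, 6, 12 and 18.

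**Late readiness.** Readiness to quit is not an inclusion criterion. The Specific Aims say that "MAPS is designed for all individuals regardless of their readiness to change", and the MAPS section accepts that "a woman not motivated to quit might negotiate the next call to occur many months later".

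**The concern.** Three conditions bar a woman from entering a trial that supplies nicotine patches and lozenges. All three can arise after entry. The plan ties supply to readiness, enrolls women who may not be ready, and repeats ST delivery at months 6 and 12. Yet the available text does not say that anyone asks about the three conditions again before supply. On that reading, a woman who was eligible at baseline and has since become pregnant, begun lactating or developed a contraindication could be sent study NRT with nobody having asked.

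What is at stake is participant safety. The comparison of the arms is not in question.

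**Working it through.** The plan gives no figure on this point, so the check sets its statements side by side and adds some simple arithmetic.

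**1. When can NRT be released?** The text allows three readings:

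| Reading | Basis | Release after baseline? |
|---|---|---|
| A. NRT with each ST delivery | NRT is a listed ST component; ST goes out at baseline, 6 and 12 months | Yes |
| B. One 12-week supply, sent when the woman becomes ready | The readiness condition, with no date limit stated | Yes, if readiness comes late |
| C. One supply mailed in the baseline packet, used when ready | Dose set at enrollment; NRT listed alongside the packet contents | No, but use may start late |

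The readiness condition and the repeated ST deliveries make A or B more likely. C cannot be ruled out.

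**2. When are the three conditions checked?** Screening and Baseline are the only marked columns in the eligibility row. The Assessments section says that Table 1 lists all measures, and none of the follow-up rows is identified as covering pregnancy, lactation or contraindication. Table 1 is not a full list of procedures, however: the Crisis Assessment described in the distress management plan has no row. The blank cells are therefore evidence of a gap but not proof.

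**3. How old is the last stated check at release?** Age of check = month of release − month of last stated check (baseline = 0).

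- Month 6 release: 6 − 0 = 6 months.
- Month 12 release: 12 − 0 = 12 months.

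**4. Should the length of the course be added?** Both patch schedules last 12 weeks: 8 + 2 + 2 = 12 for heavier smokers and 8 + 4 = 12 for lighter smokers. In months this is 84 / 30.44 = 2.76. If use starts at release and runs the full course, the baseline check is 6 + 2.76 = 8.8 or 12 + 2.76 = 14.8 months old at the end. But a check made at release would itself be 2.76 months old by then. The part that a re-check can remove is therefore 8.76 − 2.76 = 6 or 14.76 − 2.76 = 12 months.

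**5. Is there a contact at which to ask?** Yes. The month 6 and 12 deliveries already depend on a completed assessment. Only readiness that arises between assessments needs a separate contact.

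**6. Does it touch power?** No. The stated 80% (150 per group, 10% against 21.9%, two-sided 0.05) reproduces at 0.807, and none of its inputs changes.

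**The case against.** The strongest reply is that the check may exist in text that was not available. The consent pages, the appendices and the NRT educational material are natural places for pregnancy and contraindication instructions. This stands. It limits the point to what the available text states, and it could reduce the remedy to a cross-reference.

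Second, reading C means that nothing is released after baseline. This also stands as a possibility, so a reader should not infer that the plan certainly ships NRT at month 6 or 12. The statements about deferred calls and about readiness to change describe MAPS counseling. They show that late readiness is expected, but not how NRT is requested or sent.

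Third, entry criteria are not automatically continuing conditions. The same list excludes current users of cessation medication, which cannot carry forward in a trial that supplies it, and no reason is given for excluding pregnancy and lactation. So meeting an exclusion later is not in itself an error. But the patch criterion is explicitly about patch use, and asking again before supply does not require the criteria to be continuing. For the same reason, a reader might infer that NRT must always be refused in pregnancy or lactation. The documents do not settle that clinical judgement.

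Fourth, the physician-supervision clause and the educational material might be said to cover later supply. The clause is an exception within an entry criterion and covers patch contraindication only. The material, as described, deals with side effects and use. Neither states a check before release. Nor does the remark that the assigned regimen is not validated settle the matter, since it concerns the reported smoking rate.

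**Conclusion.** The point holds as a cheap patient-safety improvement. In the available text, the three conditions are checked only at Screening and Baseline, while NRT can, on the likely reading, be released later. The last stated check is then about 6 months old at a month 6 release, or 12 months old at a month 12 release. This assumes that NRT is released after baseline and that no unseen appendix or consent page requires a check.

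Two stronger inferences are not supported. One is that a known or substantial number of women would be exposed. The documents give no pregnancy rate and no count of later releases, and the number affected may be zero. The median age of 49 in the Significance section is age at cancer diagnosis. It is not age at enrollment and does not describe the dysplasia group, so it neither establishes nor excludes a risk. The other is to quote 8.8 or 14.8 months as the gap, because those figures include 2.76 months of use that a check at release could not remove.

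**What to change.** - In Nicotine Replacement and Standard Treatment (ST), say whether the 12-week supply is given once or with each ST delivery, and when it is sent.
- Before any NRT release after baseline, in both arms, repeat the existing entry questions on pregnancy, lactation and patch contraindication. Do this at the month 6 or 12 assessment call, or by brief contact if readiness arises between calls.
- If any answer is positive, hold study NRT unless a physician supervises or approves its use. Still send the quitline letter and self-help materials, and keep the woman in follow-up and in the intent-to-treat analysis.
- If NRT is mailed only once, at baseline, instead instruct women to contact staff before starting it if their status has changed.
- If an appendix or the consent form already requires a check, a cross-reference in the NRT section is enough.

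The cost is a short amendment, a few extra questions, an occasional extra contact, and some shipments delayed or withheld. The rule is the same in both arms and removes nobody from the analysis, so power and the primary analysis stay as planned.

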Reasons for Quitting (Intrinsic and Extrinsic Motivation)		X	X	X	X	X
Motivation		X	X	X	X	X
AGENCY: SENSE OF CONTROL, SELF-EFFICACY, COPING BEHAVIOR						
Sense of Control		X	X	X	X	X
Self-Efficacy Scale		X	X	X	X	X
Coping Inventory		X	X	X	X	X
STRESS, NEGATIVE AFFECT						
Perceived Stress Scale (PSS)		X	X	X	X	X
Positive and Negative Affect Scale (PANAS)		X	X	X	X	X
Depression (CES-D)		X	X	X	X	X
SMOKING-RELATED MEASURES						
Heaviness of Smoking Index (HSI)		X	X	X	X	X
Wisconsin Smoking Withdrawal Scale (WSWS)		X	X	X	X	X
Wisconsin Inventory of Smoking Dependence Motives (WISDM-37)		X	X	X	X	X
SMOKING STATUS, BIOCHEMICAL VERIFICATION, QUITLINE USE						
Smoking Status (SRNT)	X	X	X	X	X	X
Use of the Quitline Cessation Services (including Pharmacotherapy)		X	X	X	X	X
Cotinine (only among participants reporting abstinence)			X	X	X	X
PATIENT REPORTED OUTCOMES						

Functional Assessment of Cancer Therapy – Cervix Cancer (FACT-Cx)	x	x	x	x	x	x
EQ-5D (for health utilities)		x	x	x	x	x

Screening and Informed Consent Procedures. After being screened in-clinic or completing a secure online screener via REDCap, potential participants will be contacted by research staff at Moffitt Cancer Center or Stephenson Cancer Center. All eligible individuals will be invited to participate. A detailed description of the study will be provided and informed consent will be obtained. For those who agree to enroll in the study, research staff will obtain informed consent either in-person or over the phone. When participants are consented over the phone, research staff will read the informed consent document to participants and will document in our database that verbal informed consent has been obtained. A copy of the informed consent document and project materials will be provided to participants either in-person or by mail. All informed consent materials will be available in both English and Spanish. Women who decline or are ineligible will be given self-help materials and a referral to other cessation programs if they so desire.

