Assessments. Research Electronic Data Capture (REDCap) will be used to administer all questionnaires over the phone, in person, and/or via a web-based link when convenient for the participant. REDCap is a secure, web-based application designed to support data capture and utilizes a computer-administered self-interview format. This system is used in all of our current research and is designed to comply with all HIPAA regulations. Having research staff read the questionnaire items to participants will help overcome problems related to low literacy levels. Finally, we will attempt to reduce the inconvenience associated with completing assessments by providing financial compensation for participants' time. In sum, the battery of instruments comprehensively assesses our hypothesized mechanisms and associated variables of interest. A copy of each assessment instrument is included in the Appendix and all measures are listed in the Procedures Table (Table 1).

Smoking Abstinence. Abstinence assessments are based on recommendations from the Society for Research on Nicotine and Tobacco (SRNT).¹⁰⁵ We will report both prolonged and point-prevalence abstinence

at all follow-up assessment points. Prolonged abstinence refers to abstinence beginning with the initiation of treatment and including a grace period. The prolonged abstinence measure utilizes SRNT's recommendation for determining relapse (i.e., 7 consecutive days of smoking or smoking in each of 2 consecutive weeks). We will also evaluate two point-prevalence abstinence measures: 1) no smoking during the previous 7 days, and 2) no smoking during the previous 30 days. For all abstinence measures, we will analyze both completers only, and intent to treat in which smokers lost to follow-up are considered smoking. Abstinence at all follow-ups will be biochemically verified using a saliva cotinine level of <20 ng/ml.

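### The saliva cotinine cut-off of 20 ng/ml applies at every follow-up with no rule for abstinent women using the nicotine replacement offered to both arms; month 3 is the most exposed visit

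*Combined protocol and SAP*

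**What the plan says.** The verification rule, under ASSESSMENTS, Smoking Abstinence, is one flat cut-off: "Abstinence at all follow-ups will be biochemically verified using a saliva cotinine level of <20 ng/ml". Table 1 limits the test to women who report abstinence, at months 3, 6, 12 and 18. They receive a saliva kit by post after the self-report.

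The trial also supplies nicotine. TREATMENT PLAN, Nicotine Replacement: "All participants are eligible to receive a 12-week supply of nicotine patches and" lozenges. Standard Treatment (ST) includes "free nicotine replacement therapy when they are ready to quit", and MAPS is ST plus counselling, so the offer reaches both arms and the start date is left open.

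The number of supplies is unclear. Nicotine Replacement speaks of one 12-week supply and adds: "At the time of enrollment, a research staff member will determine the proper dose". The ST paragraph says: "ST will be delivered a total of 3 times to participants with completed assessments (at Baseline, 6 and 12 months".

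Three abstinence measures are to be reported: prolonged, 7-day and 30-day. The plan does not say which is primary. Missing Data and Dropouts codes missing abstinence data as smoking. It does not mention a woman who reports abstinence and returns a sample at or above the cut-off.

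**The concern.** Cotinine is formed from nicotine whatever its source. A woman who has stopped smoking and is using the patches or lozenges the trial gave her may therefore exceed the cut-off. No section exempts her, delays her sample or gives her a separate code. Use of cessation medication is addressed only as an exclusion at entry.

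If such women are counted as smoking, abstinence is understated. If their share differs by arm, the treatment effect is biased. A difference is plausible: only MAPS has counselling calls, and "call timing can be negotiated to be clustered around the timing of a specific quit attempt". The direction cannot be known in advance.

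The rule feeds the month-18 primary outcome, the mixed model over months 3 to 18, and the quitter counts in the cost-effectiveness analysis. Project Design and Procedures extends primary status further: "The primary outcomes are abstinence from tobacco at the 18-month follow-up and abstinence across all follow-ups". Under that sentence month 3 enters a primary outcome, although Specific Aims and Data Analysis Approach name month 18 alone.

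**Working it through.** **1. Timing.** Inputs: an 84-day course (12 weeks), ST mailings at baseline, 6 and 12 months, and 30.44 days per month.

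- Month 3 is day 3 × 30.44 = 91.3. A course begun at baseline ends on day 84, which is 7.3 days earlier.
- Months 6, 12 and 18 each fall 6 × 30.44 = 182.6 days after the preceding mailing. A course begun at that mailing ends 182.6 − 84 = 98.6 days before the visit.

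A full course begun more than about 7 days after baseline is therefore still running on the month-3 date. Saliva is collected later, by post. If the lag is 7 to 14 days (an assumption), that threshold moves to about 14 to 21 days. Month 3 remains the most exposed visit.

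**2. Abstinence definition.** Assume that replacement starts at the quit. A woman counted as abstinent for 7 (or 30) days must have started at least that long before the visit. The start window that overlaps the visit is then 84 − 7 = 77 days, or 84 − 30 = 54 days.

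| Visit | 7-day measure | 30-day measure |
|---|---|---|
| Month 3 | 77/91.3 = 84% | 54/91.3 = 59% |
| Months 6, 12, 18 | 77/182.6 = 42% | 54/182.6 = 30% |

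These are shares of the calendar time since the preceding mailing. They are not probabilities, because the documents give no distribution of start dates. A postal lag shortens each window by its own length.

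For prolonged abstinence at month 18, an overlapping course must start after month 18 − 84/30.44 = 15.2. That measure runs from the start of treatment plus a grace period, so a first quit that late would ordinarily not count. Exposure there is small.

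**3. The plan's power.** Inputs from Power: 150 per group, two-sided 0.05, 10% against 21.9%. With the pooled-variance test of two proportions,

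power ≈ Φ{[d√n − 1.96√(2p̄(1−p̄))] / √(p₁(1−p₁) + p₂(1−p₂))}.

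Here d = 0.119 and p̄ = 0.1595, so power = Φ{(1.457 − 1.015)/0.511} = Φ(0.866) = 0.807. The stated 80% is reproduced. The odds ratio is (0.219/0.781)/(0.10/0.90) = 2.52.

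**4. Hypothetical loss.** Let q be the share of abstainers who fail only because of nicotine replacement. Assume that failures are coded as smoking and that the planning rates are rates before verification. Each observed rate is then the planned rate × (1 − q). Expected abstainers number 150 × 0.10 + 150 × 0.219 = 47.85.

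| q in ST | q in MAPS | Observed rates | Difference (points) | Odds ratio | Power |
|---|---|---|---|---|---|
| 0 | 0 | 10.0% vs 21.9% | 11.9 | 2.52 | 0.81 |
| 5% | 5% | 9.5% vs 20.8% | 11.3 | 2.50 | 0.78 |
| 10% | 10% | 9.0% vs 19.7% | 10.7 | 2.48 | 0.76 |
| 20% | 20% | 8.0% vs 17.5% | 9.5 | 2.44 | 0.70 |
| 10% | 20% | 9.0% vs 17.5% | 8.5 | 2.15 | 0.59 |
| 20% | 10% | 8.0% vs 19.7% | 11.7 | 2.82 | 0.84 |

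The equal-q rows correspond to 47.85q = 2.4, 4.8 and 9.6 women failing in total. With no true effect (10% in both arms), q of 5% against 10% gives a rejection rate of 5.3%, and 20% against 10% gives 6.1%.

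**The case against.** The strongest defence is that the plan already deals with validation. It follows the recommendations of a nicotine research society, concedes that cotinine cannot validate every definition, and cites misreporting of about 2%. Table 1 also collects "Use of the Quitline Cessation Services (including Pharmacotherapy") at each follow-up, and the instruments are in an Appendix not reviewed here. This does not close the gap. A truthful abstainer on nicotine replacement is not misreporting. The Table 1 item concerns quitline services, and nothing ties it to the cotinine decision. The only verification rule written down is the flat cut-off. An Appendix instrument may already record use at the sample date, in which case the fix is cheaper.

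Several limits do stand:

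- q has no source, and the documents give no saliva levels for patch or lozenge users. Overlap with a course is not the same as failing the test, and the patch regimen steps down.
- The Power section does not say whether 10% and 21.9% are rates before or after verification. If after, the design may already absorb the loss.
- Coding a failed test as smoking is an assumption.
- Keeping the strict rule as primary is defensible, provided the alternative is prespecified.

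A reader might infer that the month-18 comparison is biased, or that the trial is underpowered. The documents support neither. They establish an unaddressed route to misclassification, but not how many women take it or in which arm.

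**Conclusion.** The concern holds as a gap in the verification rule. The plan offers nicotine to both arms and verifies abstinence with a marker that nicotine raises, without saying how the women caught between the two are classified. Month 3 is the most exposed visit, an inference from the supply schedule and not from usage data. Months 6, 12 and 18 are exposed only through later starts, to a degree that depends on the abstinence definition.

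The size is unknown. On the stated assumptions the loss of power is modest when q is small and equal by arm. A ten-point difference in q shifts the odds ratio noticeably, in either direction. A reader might take the calendar-time shares as the proportion of women affected. They are not: they assume that replacement starts at the quit and that a full course is used, and they carry no information on when women start. The point should be fixed because the remedy is cheap and because, left open, the coding could be decided after results are seen.

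**What to change.** Amend Smoking Abstinence as follows.

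1. Record use of any nicotine product, and the date of last use, with each saliva sample, unless an existing instrument already does so.
2. Prespecify that, for a self-reported abstainer who reports such use at sampling, cotinine of 20 ng/ml or more does not by itself overturn her self-report. For all other self-reported abstainers it counts as smoking.
3. Report the strict cut-off for everyone as a sensitivity analysis. If the sponsor prefers the strict rule as primary, the product-aware analysis should be the prespecified sensitivity analysis.
4. Tabulate nicotine-product use by arm and visit.
5. Reconcile the Nicotine Replacement and ST paragraphs on whether the 12-week supply is given once or with each ST mailing, so that exposure at the later visits can be judged.

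The cost is a wording change, one further analysis, one table and possibly one short question with the kit. The downside is that self-report goes unverified among users, which could favour the arm using more nicotine replacement; the strict analysis shows how far the result depends on this. The rule cannot be applied to samples already collected without the usage record. A repeat sample after replacement ends, or a marker it does not affect, would verify these women but needs new procedures.
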